## Research Question/Hypothesis

- Research Question: Will preterm neonates with estimated gestational age of 26 0/7 to 32 6/7 gestation who are supplemented with iron on an every-other-day (EOD) dosing, compared to those who are supplemented with iron daily, have the same incidence of achieving iron replete status (reticulocyte-Hb >29) at 36 weeks post-menstrual age (PMA)?
- Hypothesis: We hypothesize that at the same dosage in oral form, there will be no difference in the incidence of preterm neonates achieving iron replete status as measured by reticulocyte hemoglobin (Ret-Hb) between EOD and daily iron supplementation.

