## METHODOLOGY

### Study design

- This is a non-inferiority, blinded, randomized control trial designed to investigate if EOD iron is comparable to daily iron dosing in achieving iron replete status by Ret-Hb measurements in premature infants.

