### Intervention

- The control group / current standard for iron supplementation in neonates is detailed as follows: after the infant achieves full enteral feeds, the infant is started on 6 mg/kg of oral iron daily supplementation. Though the American Academy of Pediatrics and World Health Recommendation recommend 2 – 4 mg/kg of supplemental iron for premature infants, studies examining the effects of higher dose of enteral iron supplementation (3.4 mg/kg to 7.1 mg/kg per day) revealed no differences between the lower versus higher dosages on morbidity (sepsis, necrotizing enterocolitis, or enteral feeding intolerance) and mortality outcomes. The dose of 6 mg/kg of enteral iron was chosen based on the aforementioned recommendations with evidence of its safety, while minimizing the need to increase the enteral iron dosage if an infant were to be started on ESAs where a dose of 6 mg/kg of enteral iron supplementation is the standard practice. Phlebotomy to obtain a complete blood count, reticulocyte count, and reticulocyte hemoglobin count is pursued the Monday after iron supplementation is started and every 2 weeks thereafter to monitor hematocrit or hemoglobin levels and iron status.

- The intervention group for EOD iron supplementation in neonates is as follows: after the infant achieves full enteral feeds, the infant is started on 6mg/kg of oral iron supplementation administered every other day. Phlebotomy to obtain a complete blood count, reticulocyte count, and reticulocyte hemoglobin count is pursued the Monday after starting iron supplementation and every 2 weeks thereafter to monitor hematocrit or hemoglobin levels and iron status. There is literature revealing that neonates even <29 weeks' gestation absorb and regulate iron similar to adults. There is literature revealing that there is no difference between EOD and daily iron supplementation in older pediatric populations and adults in improving hemoglobin levels, with one study in Switzerland revealing that EOD iron reduced iron deficiency in the longer term and triggered fewer gastrointestinal side effects in adult women. Given the evidence that premature infants regulate their iron status similarly to older infants and adults, and the current evidence of EOD iron in older children and adults, this intervention, compared with our control, will help us address our primary question to determine if EOD iron is non-inferior to daily iron.

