## Data Analysis

- A sample size determination was conducted using Riskcalc.org (Chow S-C, Shao J, Wang H, Lokhnygina Y. Sample Size Calculations in Clinical Research. Third ed: Chapman and Hall/CRC; 2017.) and confirmed by [name] (BAMC Statistician). Sample size estimates are for type 1 error of 5% ( $\alpha = 0.05$ ), power ( $1-\beta$ ) of 80%, ratio of 1:1 of intervention to control. The effect size is determined by estimating the proportion of infants with Ret-Hgb >29 pg to be similar at 80% between daily versus EOD iron, with a margin of 20%. It was determined that a sample size of 100 patients would be needed for this study (50 for intervention, and 50 for control).
- A statistician who is blinded to the study allocation will analyze the data. All statistical analyses will be performed with IBM SPSS Statistics (Armonk, NY: IBM Corp) and JASP Team (2022). JASP, Version 0.16.1 (Netherlands: JASP Team). Descriptive statistics will be performed for all variables. Categorical data will be reported as percentages, and continuous data will be reported as medians with interquartile range or means with standard deviation. The two groups will be compared according to the intention to treat with the use of Student's t-tests, Mann-Whitney-U tests, chi-square analysis based on the outcome being evaluated. All p-values will be one-sided, with a statistical significance level of <0.05. Covariates to include gestational age, in-born versus out-born infants, ESA use, receipt of pRBC transfusion will be controlled for using a logistic regression model and will be reported with an odds ratio (OR) and 95% confidence intervals (CI). A medical monitor who is not involved in the study will be assigned prior to the initial enrollment of the trial to monitor the data periodically (every 3 months) to ensure the safety of the participants and the scientific integrity of the study. An interim analysis will be performed at halfway to target enrollment.

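### The trial is sized for non-inferiority on a 20-point margin, but no analysis named for the binary primary endpoint uses that margin

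*Protocol*

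**What the plan says.** Study design states the aim: "This is a non-inferiority, blinded, randomized control trial". Intervention repeats it, describing the "primary question to determine if EOD iron is non-inferior to daily iron". The primary endpoint is binary: iron replete or not, by Ret-Hb >29 pg, at 36 weeks PMA.

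Data Analysis sizes the trial by taking the replete proportion "to be similar at 80% between daily versus EOD iron, with a margin of 20" percent, with type 1 error 5%, power 80% and 1:1 allocation. The result is 100 infants, 50 per arm. This is the only place where the margin appears.

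The analysis paragraph that follows has three elements:

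- Tests: the groups are "compared according to the intention to treat with the use of Student's t-tests, Mann-Whitney-U tests, chi-square analysis based on the outcome being evaluated".
- Level: "All p-values will be one-sided, with a statistical significance level of <0.05".
- Estimate: a logistic regression on named covariates, whose results "will be reported with an odds ratio (OR) and 95% confidence intervals (CI".

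Research Question/Hypothesis puts the hypothesis as "there will be no difference in the incidence of preterm neonates achieving iron replete status", without a margin.

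**The concern.** A non-inferiority claim needs the data to exclude a loss as large as the margin. A test of zero difference does not do that: a non-significant result may only mean that the trial is too small to see a loss that matters. Here the endpoint, margin and alpha are all stated, but nothing joins them into a decision.

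Two features make the gap worse. The one-sided rule covers every p-value but gives neither a direction nor a margin-shifted null. The hypothesis of no difference invites the reader to take a non-significant test as success.

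What is at stake is the primary conclusion, which would depend on a reading chosen once the data are known. The Protocol's own risk section lists anemia and neurodevelopmental impairment among the consequences of iron deficiency, so a false claim of comparability matters.

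The concern is limited to the primary endpoint. Difference tests are ordinary for the secondary outcomes.

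**Working it through.** **1. Reproduce the sample size.** Inputs from Data Analysis: 80% in both arms, margin 0.20, alpha 0.05, power 80%.

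n per arm = (1.645 + 0.842)² × (2 × 0.8 × 0.2) / 0.2² = 49.5, so 50 per arm and 100 in total. The stated figure reproduces as non-inferiority on an absolute 20-point margin at one-sided 0.05.

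Other readings do not give it:

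| Reading | n per arm |
|---|---|
| Non-inferiority, one-sided 0.025 | 63 |
| Margin 20% relative (16 points), one-sided 0.05 | 78 |
| Equivalence by two one-sided tests at 0.05 | 69 |
| Superiority, 80% vs 60%, one-sided / two-sided | 64 / 82 |

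The sizing therefore depends on a margin that the analysis text never uses.

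**2. Can the odds ratio carry the margin?** The odds ratio for a 20-point loss depends on the daily-arm rate:

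- 90% vs 70%: (0.7/0.3)/(0.9/0.1) = 0.26
- 80% vs 60%: (0.6/0.4)/(0.8/0.2) = 0.375
- 70% vs 50%: (0.5/0.5)/(0.7/0.3) = 0.43

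The margin does not translate into one odds ratio. A 95% CI also corresponds to one-sided 0.025, not the 0.05 used for sizing.

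**3. A concrete conflict.** Take daily 40/50 and EOD 36/50.

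- Chi-square: pooled proportion 0.76; z = -0.08 / √(2 × 0.76 × 0.24 / 50) = -0.08/0.0854 = -0.94; one-sided p = 0.17, not significant.
- Newcombe 90% interval (Wilson limits with z = 1.645): EOD lower limit 0.606, daily upper limit 0.877. Lower limit of the difference = -0.08 - √[(0.72 - 0.606)² + (0.877 - 0.80)²] = -0.08 - 0.137 = -21.7 points. The margin is not excluded.

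With daily fixed at 40/50:

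| EOD replete | One-sided chi-square p | Lower 90% limit (points) | Non-inferior? |
|---|---|---|---|
| 32/50 | 0.037 | -29.9 | no |
| 33/50 | 0.057 | -27.9 | no |
| 36/50 | 0.174 | -21.7 | no |
| 37/50 | 0.238 | -19.6 | yes |

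From 33 to 36 the test finds no significant difference, and non-inferiority is not shown.

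**4. Operating characteristics.** These come from exact binomial enumeration over all 51 × 51 outcomes, with 50 evaluable infants per arm, uncorrected chi-square and the Newcombe limit.

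| True daily / EOD | Chi-square non-significant for EOD worse | Lower 90% limit above -20 points | Non-significant, margin not excluded |
|---|---|---|---|
| 80% / 80% | 95.0% | 81.1% | 13.9% |
| 80% / 70% | 68.5% | 33.4% | 35.1% |
| 80% / 60% | 28.0% | 5.4% | 22.6% |

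At 80%/60% the Miettinen-Nurminen limit passes 5.1% of trials. A two-sided chi-square is non-significant in 40.5%.

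If the daily rate is not 80%, a true 20-point loss is non-significant (one-sided) in 17.7% of trials at 90 vs 70, 23.8% at 85 vs 65, 30.7% at 75 vs 55 and 34.2% at 70 vs 50.

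If instead a significant result in favour of EOD were required, success at equal 80% rates would be 5.0%.

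**The case against.** The strongest reply is that this is a missing linking sentence rather than a wrong method. The design, endpoint, margin and alpha are all stated, and a statistical analysis plan that is not at hand could supply the interval method and the formal hypotheses. One-sided 0.05 matches the sizing exactly, which suggests that a margin test was intended. The list of tests is generic and never assigns chi-square to the primary endpoint by name. The odds ratio is described as covariate control, so it needs a margin only if it is primary. The 28% and 5% figures rest on decision rules that the Protocol does not state, and the 13.9% at equal rates is part of the ordinary type II error of a correct non-inferiority test.

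Much of this is fair as qualification. That chi-square applies is an inference, made because no other listed unadjusted test fits a binary outcome. The 28% and 5% are conditional and should be read so. The 13.9% is not an error rate: it shows how often the two readings would part.

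The core remains. The Protocol does not leave the analysis open. It names the tests, the sidedness, the model and the estimate, and none of them uses the margin. A separate plan could cure this only by adding a primary analysis that the Protocol does not list. One-sidedness without a direction or a shifted null still tests zero difference.

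**Conclusion.** The concern holds and must be fixed, because it affects the trial's primary decision rule. Followed as written, the Data Analysis section does not answer the declared non-inferiority question.

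The sample size is not in error. The loss lies in what the result would mean. Under one natural reading of the named test, the false-claim rate at a true 20-point loss is 28% rather than about 5%. Under the other, the chance of success at equal rates is about 5% rather than about 80%.

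These figures assume 50 evaluable infants per arm, a daily rate of 80% where not varied, an uncorrected chi-square, and no alpha spent at the planned interim analysis. The mismatch between sizing and analysis does not depend on those assumptions.

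**What to change.** In Data Analysis, state the primary analysis: the difference in the proportion with Ret-Hb >29 pg at 36 weeks PMA, EOD minus daily. Non-inferiority is concluded only if the lower one-sided 95% confidence limit (the lower end of a two-sided 90% interval, by Newcombe or Miettinen-Nurminen) is above -20 percentage points. Add that a non-significant chi-square is not evidence of non-inferiority. Keep the difference tests for secondary outcomes and the adjusted odds ratio as supportive.

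In Research Question/Hypothesis, restate the hypotheses as H0: difference ≤ -20 points against H1: difference > -20 points.

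The cost is wording in two sections, with no extra patients, visits or data. The sample size stays at 100 and power at about 80% (81.1% with Newcombe, 80.5% with Miettinen-Nurminen), given the Protocol's own premise of 50 evaluable infants per arm. Only if the team based the decision on a two-sided 95% interval would power need restating, as about 71%; 80% power would then take 126 infants.

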## Objectives

- Primary objective: determine if daily versus EOD oral iron at the same dose per kilogram per day will achieve similar incidence of iron replete status at 36 weeks PMA.
- Secondary objective:
  - Characterize Ret-Hb levels in preterm infants
  - Identify the number of blood transfusions received between enrollment and 36 weeks' PMA between two groups
  - Determine prevalence of bronchopulmonary dysplasia between two groups
  - Identify the number with sepsis (defined as a positive blood or cerebrospinal fluid culture that was treated with antibiotics for at least 7 days) between two groups
  - Identify the number with necrotizing enterocolitis (NEC)/gastrointestinal perforation (medical NEC defined as  $\geq$ stage II Bell's criteria between two groups
  - Characterize growth (assessed by length gain at 36 weeks' PMA or at discharge if discharged before 36 weeks) between two groups

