## Identified Risks/Ethical Considerations

- The risks associated with iron deficiency include anemia (and associated symptoms to include tachycardia, tachypnea, increased oxygen requirement, increased apnea/bradycardia/desaturation events which can lead to unnecessary evaluations for sepsis and antibiotic administration), long-term neurodevelopmental impairment, increased risk for necrotizing enterocolitis, packed red blood cell (pRBC) transfusion and transfusion-related risks, as well as delayed growth. The overall risk of iron deficiency will be mitigated by monitoring the complete blood count and reticulocyte count for hemoglobin/hematocrit levels and Ret-Hb levels every two weeks. There is no evidence to suggest EOD

iron dosing will result in worse outcomes compared to daily iron dosing. However, outcomes will be monitored every three months to ensure there are no significant adverse outcomes which would warrant study cessation.

- Current practice for frequency of phlebotomy varies by institution but the recommended frequency of lab draws in this study are within normal standards for preterm infants of this gestational age.
- A medical monitor who is not involved in the study will be assigned prior to the initial enrollment of the trial to monitor the data periodically (every 3 months) to ensure the safety of the participants and the scientific integrity of the study.

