### **Benefits of Proposed Research to the Subjects and Others (significance of your study)**

- This will give us insight if EOD iron is equivalent to daily iron supplements. This may also benefit hospital costs as it can help reduce total iron utilization for the duration of the neonate's hospitalization. This study may also help researchers and clinicians gain insight if EOD iron is as efficacious as daily iron in achieving iron replete status in premature infants with the potential of minimizing the side effects of oral iron intake. Participants will not receive compensation for participating in this trial.

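### The one-sided 0.05 rule matches the primary non-inferiority sizing but is extended to every p-value, including secondary comparisons with no stated direction, and does not match the 95% level of the regression intervals

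*Protocol*

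**What the plan says.** The Study design section sets a non-inferiority aim: "This is a non-inferiority, blinded, randomized control trial designed to investigate if EOD iron is comparable to daily iron dosing". The Data Analysis section sizes the trial with a 5% type 1 error, 80% power, 80% iron-replete in both arms and a 20% margin, giving 50 per arm.

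The same section then says the groups will be compared by t-tests, "Mann-Whitney-U tests, chi-square analysis based on the outcome being evaluated". The next sentence is "All p-values will be one-sided, with a statistical significance level of <0.05". No outcome is excepted. The sentence after that turns to a logistic regression adjusting for four covariates, whose result "will be reported with an odds ratio (OR) and 95% confidence intervals (CI" (95% intervals, with no mention of a one-sided bound).

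The secondary objectives are worded without direction, for example "Determine prevalence of bronchopulmonary dysplasia between two groups" and "Characterize growth (assessed by length gain at 36 weeks". Transfusions, sepsis and NEC or perforation are likewise only to be compared between the groups.

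**The concern.** A one-sided p-value has no meaning until a direction is named, and the ordinary chi-square test has none. For the primary outcome the non-inferiority hypothesis supplies the direction. For the secondary outcomes nothing does, and the protocol gives grounds for both directions. Identified Risks/Ethical Considerations lists among the risks of iron deficiency "increased risk for necrotizing enterocolitis, packed red blood cell (pRBC) transfusion and transfusion-related risks, as well as delayed growth", so every-other-day (EOD) dosing might do worse. The section on benefits speaks of EOD iron "with the potential of minimizing the side effects of oral iron intake", so it might do better.

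At stake is how the secondary results can be read. A difference in the untested direction could go undeclared. A difference could also be called significant at a level that most readers will take to be two-sided. Separately, an adjusted odds ratio could be called significant beside a 95% interval that includes 1.

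**Working it through.** **1. The plan's own figure.** Inputs from Data Analysis: 80% in both arms, margin 0.20 (read as percentage points, because this reproduces N), power 80%, 1:1 allocation.

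n per arm = (z_alpha + z_beta)² × 2 × p(1 − p) / margin²

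- One-sided 0.05: (1.645 + 0.842)² × 2 × 0.8 × 0.2 / 0.2² = 49.5, so 50 per arm and 100 in total. This matches the protocol.
- One-sided 0.025: (1.960 + 0.842)² × 0.32 / 0.04 = 62.8, so 63 per arm. This does not match.

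One-sided 0.05 is therefore the level at which the primary comparison was sized.

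**2. Secondary outcomes, direction fixed in advance.** 50 per arm. The protocol gives no event rates, so null rates of 5%, 10%, 15%, 20% and 30% are assumed. The figures come from exact enumeration of both binomial distributions.

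- Error in the tested direction: 4.8% to 6.0% for the uncorrected chi-square, 1.1% to 3.2% for Fisher. The nominal 5% is essentially kept.
- Chance of declaring a true difference of 10% against 30%:

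| Test | One-sided, tested direction | One-sided, other direction | Two-sided 0.05 |
|---|---|---|---|
| Uncorrected chi-square | 82.3% | 0.001% | 73.4% |
| Fisher | 74.8% | 0.0004% | 64.0% |

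- Growth by t-test (98 degrees of freedom), true difference 0.5 SD: 79.9% in the tested direction, 0.002% in the other, 69.7% two-sided.

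**3. Secondary outcomes, direction taken from the data.** This is a conditional case; the protocol does not say it will be done. Error under no true difference, same assumed rates in order:

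| Test | One-sided 0.05, direction from data | Two-sided 0.05 |
|---|---|---|
| Uncorrected chi-square | 11.9, 10.4, 9.6, 10.0, 10.4% | 4.3, 5.1, 5.5, 5.2, 5.0% |
| Fisher | 2.2, 4.9, 5.6, 5.8, 6.4% | 0.7, 1.8, 2.4, 2.8, 3.1% |
| t-test | 10.0% | 5.0% |

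The error roughly doubles for the t-test and the uncorrected chi-square. For Fisher, which the protocol does not name, the absolute error stays at or below 6.4%. The larger Fisher ratios at low rates partly reflect discreteness.

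**4. Regression odds ratios.** One-sided 0.05 has critical value 1.645 and corresponds to a two-sided 90% interval. A two-sided 95% interval uses 1.960 and corresponds to one-sided 0.025. If an odds ratio is tested against 1, results with z between 1.645 and 1.960 in the tested direction are significant by the rule while the 95% interval includes 1.

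Illustration with assumed values, OR 2.5 and SE(log OR) 0.5:
- z = ln(2.5)/0.5 = 0.916/0.5 = 1.83, one-sided p = 0.033.
- 95% interval: exp(0.916 ± 1.960 × 0.5) = 0.94 to 6.66, which includes 1.
- 90% interval: exp(0.916 ± 1.645 × 0.5) = 1.10 to 5.69, which excludes 1 and agrees with the p-value.

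**The case against.** The strongest defence is that one-sided testing belongs in a non-inferiority trial, and that a natural direction for the secondary outcomes is EOD worse. With that direction fixed beforehand the error is held near 5%, and harm from EOD dosing is detected with more power than a two-sided test gives (82% against 73% for 10% against 30%). Only an EOD benefit would go undeclared. This stands as far as it goes. A reader might infer that the rule doubles the false-positive rate, or that it hides harm from EOD dosing. The protocol supports neither as a general statement: the first needs the direction to be read off the data, and the second needs it to be fixed towards EOD benefit. But the protocol names no direction, and its own text points both ways, so the defence rests on a choice it does not make.

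On the intervals, a reader might infer a flat contradiction. That is too strong. The protocol does not say the odds ratio will be tested against 1, nor which outcome the model serves. If the model is an adjusted analysis of the primary outcome judged against a margin, an interval including 1 contradicts nothing. If a one-sided bound was meant, the mismatch disappears, but the text does not say so. What remains is a mismatch of levels with a conditional consequence.

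It may also be said that a statistical analysis plan could settle direction. A missing direction alone could be left there. A rule covering every p-value is already fixed in the protocol, and a later plan using two-sided secondary tests would contradict it. Nor does the three-monthly review by the medical monitor settle how final comparisons are declared.

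**Conclusion.** The point holds as a defect of scope and of matching levels. One-sided 0.05 agrees with the sizing of the primary comparison; that agreement concerns the level and N only, since the tests listed are ordinary difference tests and the text does not say how the margin enters. Extending the level to all p-values leaves the secondary comparisons without a defined test.

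The size depends on the reading. With a direction fixed in advance, the loss is the other direction: under 0.1% against 73% two-sided (64% Fisher) for 10% against 30%. With a direction taken from the data, the error would be about 10% against 5% for the t-test and uncorrected chi-square, and lower in absolute terms for Fisher. The interval mismatch affects only odds ratios tested against 1 with one-sided p between 0.025 and 0.05. The event rates, the 0.5 SD difference and the example odds ratio are assumptions.

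Nothing here shows that the sample size is wrong. The wording should be corrected before analysis.

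**What to change.** Replace the blanket sentence in Data Analysis with two:

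- One-sided 0.05 applies only to the primary non-inferiority test, reported with its matching one-sided 95% bound (equivalently a two-sided 90% interval) for the difference in proportions, set against the 20% margin.
- All secondary outcomes, and covariate-model odds ratios tested for a difference, use two-sided p-values at 0.05 with two-sided 95% intervals.

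The total of 100 does not change, because only the primary test drives it. The cost is lower power for secondary outcomes than a correctly directed one-sided test would have: for 10% against 30%, from 82% to 73% (uncorrected chi-square) or 75% to 64% (Fisher); for a 0.5 SD difference in growth, from 80% to 70%. If the sponsor instead wanted the primary conclusion to rest on a two-sided 95% interval, the same formula gives 63 per arm, 126 in total, and 50 per arm would have about 70.5% power. The correction does not require that.

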### **Data Collection**

- The electronic medical records of CHRISTUS and Brooke Army Medical Center (BAMC) will be queried for patients who meet inclusion criteria as described above and consented for participation in the trial. Patient demographic information will be collected, along with other variables as outlined below:
  - Maternal Information
    - Age
    - Race / ethnicity: non-Hispanic White, non-Hispanic Black, Hispanic, Asian/Pacific Islander, Native
    - For patients at BAMC:
      - Mother Active Duty, Non-Active Duty, Retired
      - Rank of Active Duty: Enlisted versus Officer
    - Past medical history such as anemia, diabetes, mood disorder, hypertension, and more
    - Prenatal laboratory history: result of hepatitis B, syphilis, HIV, GBS status, blood type, rubella and varicella immunity status, gonorrhea and chlamydia status
    - Medication history to include use of antidepressants, anticonvulsants, insulin, aspirin, iron supplementation
    - Complications during delivery such as postpartum hemorrhage (>500 mL vaginal delivery, >1000mL c-section), magnesium around labor/delivery time-period, required pRBC transfusion
    - Blood type, antibody status

- Hemoglobin, hematocrit results prior to delivery
- Neonatal Information
  - Gestational age at birth
  - Birth order (first born, not first born)
  - Weight at birth
  - Delivery method: vaginal versus cesarean section
  - Instrumentation at delivery: vacuum assisted, forceps assisted, none
  - Race / ethnicity: non-Hispanic White, non-Hispanic Black, Hispanic, Other, Asian/Pacific Islander, Native
  - Phototherapy requirement
  - Blood type, DAT status
  - Delayed cord clamping
  - Hemoglobin, hematocrit, mean corpuscular volume at:
    - T0= first lab draw following starting iron
    - T1 = 2 weeks following T0
    - T#= every 2 week intervals until 36 weeks PMA or discharge
  - reticulocyte count, reticulocyte hemoglobin at:
    - T0= first lab draw following starting iron
    - T1 = 2 weeks following T0
    - T#= every 2 week intervals until 36 weeks PMA or discharge
  - Change in hematocrit, hemoglobin, retic count, retic hemoglobin between end of trial and T0
  - Ferritin, Serum TIBC, and iron levels at 36 weeks PMA
  - Darbepoetin / EPO use
  - Number of pRBC transfusions

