  - Neonatal morbidities documented in the EMR which includes include anemia defined by unit guidelines based on the neonate's clinical status and corrected gestational age, necrotizing enterocolitis, sepsis, chronic lung disease, intubation, death, feeding difficulties
  - Neonatal severity scoring (NSOFA) at start of trial (T0) and every 2 weeks thereafter (T#)
  - Type of feed and calories from T0 to T#
  - Feeding volume at T0 to T#
  - Weekly growth parameters T0 to T# (weight, length, and head circumference)
  - Type of respiratory support T0 to T#
  - Blood draw volume T0 to T#
  - Transfusions from T0 to T#
  - Presence of specific diagnosis: constipation, feeding intolerance, infectious screen, clinical sepsis
- Data collected will include MRN; however, this will not be used in the analysis. All data will be deidentified before they are entered into REDCap for effective safeguard of information. Personnel

identified in this protocol will be responsible for collecting the data and will be the only persons who will have access to the de-identified data inputted on REDCap for further management and analysis.

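### The adjusted logistic model controls for transfusion (and ESA use) with no pre-randomisation limit, although transfusion after enrolment is itself a trial outcome

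*Protocol*

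**What the plan says.** The Data Analysis section lists four covariates for the adjusted model: gestational age, in-born or out-born status, ESA use and receipt of packed red cell (pRBC) transfusion. Of the last two it says "ESA use, receipt of pRBC transfusion will be controlled for using a logistic regression model", and the result is to be an odds ratio with a 95% confidence interval. Neither covariate has a time window. The same paragraph states that "The two groups will be compared according to the intention to treat", using t-tests, Mann-Whitney U tests and chi-square tests.

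Four other places bear on the timing:

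- Objectives, secondary: "Identify the number of blood transfusions received between enrollment and 36 weeks' PMA between two groups".
- Identified Risks/Ethical Considerations: the listed risks of iron deficiency include "packed red blood cell (pRBC) transfusion and transfusion-related risks".
- Data Collection: one item is "Number of pRBC transfusions", with no window. Another is "Transfusions from T0 to T" (T#, the later two-weekly time points). The start point is defined as "T0= first lab draw following starting iron".
- Intervention: one reason given for the chosen dose is "minimizing the need to increase the enteral iron dosage if an infant were to be started on ESAs". The protocol thus foresees ESAs starting after iron has started.

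**The concern.** A covariate that treatment can change should not be in the model that estimates the treatment effect. If every-other-day (EOD) dosing lowers iron status, and lower iron status leads to more transfusion, then holding transfusion fixed removes or distorts part of the effect the trial is meant to measure. Transfusion may also share unmeasured causes with reticulocyte haemoglobin (Ret-Hb), such as general illness. Conditioning on it can then create an apparent arm difference where there is none.

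In a non-inferiority trial, a shift of the OR towards or past 1 favours the claim being tested. The adjusted OR is also the only effect estimate for which the Data Analysis section names a confidence interval. If it disagrees with the unadjusted comparison, a reader could not tell whether the cause is baseline imbalance or the choice of covariate.

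**Working it through.** **The plan's own figure.** Sample size for a difference in proportions, with 80% in both arms, margin 0.20, one-sided alpha 0.05 and power 80%:

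n per arm = (z₀.₉₅ + z₀.₈₀)² × 2p(1−p) / margin² = (1.645 + 0.8416)² × 0.32 / 0.04 = 6.183 × 8 = 49.5, so 50 per arm and 100 in total.

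This matches the protocol. At 50 per arm, SE = √(0.32/50) = 0.08, and power = Φ(0.20/0.08 − 1.645) = Φ(0.855) = 80.4%. The sample size rests on an unadjusted difference, so the covariate choice does not alter it.

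**Can the data items supply a pre-randomisation covariate?** The untimed transfusion count mixes transfusions before and after randomisation. The count from T0 begins after iron has started, so it is wholly post-randomisation. Subtracting the second from the first leaves transfusions before T0, which still includes the days between starting iron and T0. No listed item isolates exposure before randomisation.

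**Illustration 1: does adjustment move the OR?** All parameters are assumed, with 1,000,000 simulated infants in total. A = 1 for EOD, U is an unmeasured standard normal frailty, M is transfusion and Y is replete status.

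- logit P(M) = −1.1 + bA + U
- logit P(Y) = 1.6 + dA + tM − U

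| b | d | t | Transfused, daily / EOD | Replete, daily / EOD | OR without M | OR with M |
|---|---|---|---|---|---|---|
| 0.7 | 0 | −0.7 | 28.7% / 41.8% | 75.4% / 73.7% | 0.92 | 1.11 |
| 0.7 | −0.4 | −0.7 | 28.6% / 41.7% | 75.2% / 67.0% | 0.67 | 0.78 |
| 0.7 | 0 | 0 | 28.5% / 41.7% | 79.4% / 79.4% | 1.00 | 1.11 |
| 0.7 | −0.4 | 0.7 | 28.6% / 41.8% | 82.6% / 78.4% | 0.77 | 0.78 |
| 0.7 | 0 | 0.7 | 28.6% / 41.8% | 82.5% / 83.6% | 1.08 | 1.10 |
| 0 | 0 | −0.7 | 28.6% / 28.6% | 75.4% / 75.3% | 1.00 | 1.00 |

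In the third row the regimen has no effect on repletion, yet the adjusted OR is 1.11. In the last row the regimen does not affect transfusion, and adjustment does nothing.

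**Illustration 2: a true deficit equal to the margin.** Assume 80% v 60% replete. The true OR is (0.6/0.4)/(0.8/0.2) = 0.375 and the true difference is −20 points. Mid-study iron is lower in the EOD arm by z₀.₈₀ − z₀.₆₀ = 0.842 − 0.253 = 0.588 SD, and carries weight 0.7 on final latent Ret-Hb. Transfusion propensity has correlation ρ in size with low iron. Transfusion shifts latent Ret-Hb by τ SD. Daily-arm transfusion is 20% or 40%. Gestational age, in-born status and ESA use are left out.

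Check on transfusion in the EOD arm when the daily arm has 40%: for ρ = 0.7, Φ(−0.253 + 0.7 × 0.588) = Φ(0.159) = 56%; for ρ = 0.4, Φ(−0.253 + 0.4 × 0.588) = Φ(−0.018) = 49%.

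The OR and standardised difference below are large-sample values (1,000,000 per arm). The false-clearance rates come from 6,000 trials of 50 per arm, tested at one-sided 5% against an OR margin of 0.375. That margin is assumed, because the protocol gives none on the OR scale.

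| ρ | τ | Adjusted OR | Standardised difference | False clearance, adjusted | False clearance, unadjusted |
|---|---|---|---|---|---|
| 0.7 | 0 | 0.436 | −15.4 points | 9.0% | 5.3% |
| 0.4 | 0 | 0.394 | −18.5 points | 5.6% | 4.9% |
| 0.4 | +0.5 | 0.372 | −20.2 points | 4.5% | 5.0% |
| 0.4 | +1.0 | 0.323 | −22.1 points | 2.5% | 5.1% |
| 0 | 0 | 0.378 | −19.9 points | 5.2% | 5.4% |

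The table shows 40% daily-arm transfusion. Over all linked settings (ρ 0.4 or 0.7; τ −0.5, 0, +0.5 or +1.0; both transfusion rates), the adjusted OR ran from 0.32 to 0.44 and the difference from −22 to −13 points. The −13 end comes from ρ = 0.7 with τ = −0.5. False clearance ran from 2.5% to 9.0% adjusted, against 4.4% to 5.6% unadjusted. With no link the difference stayed at −20 points and adjusted false clearance was 3.1% to 5.2%.

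The result depends on the assumed pathway. If the regimen acts wholly through mid-study iron, ρ = 0.7 with τ = 0 gives OR 0.48 and −13.7 points, and ρ = 0.4 with τ = +1.0 gives 0.30 and −23.2 points.

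**The case against.** The strongest reply is that the covariate window and the choice of deciding analysis are details usually left to a statistical analysis plan, which may exist and is not at hand. Receipt of transfusion might have been meant as exposure before enrolment, which is a proper covariate. The only margin in the protocol is on the proportion scale, the sample size reproduces from an unadjusted difference, and the intention-to-treat comparison is named first. The logistic model may therefore be only supportive. Transfusions can also be dated from the medical record, and two separate transfusion items suggest two windows.

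Part of this stands. The unadjusted comparison is untouched, and the harm reaches the conclusion only if the adjusted OR is used for it. But the protocol does not leave the covariates open: it names them, and it names one that it elsewhere treats as an outcome and as a risk of iron deficiency. That is a stated choice, not an omitted detail. The record could supply dates, but the listed items do not ask for them.

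A second objection concerns the false-clearance rates. The 0.375 margin is a marginal OR applied to a conditional one, and odds ratios are non-collapsible. This is fair, and it shows in the no-link rate of 3.1% where there is no bias. The standardised differences avoid the problem and are the better guide. It is also true that at ρ = 0.4 the effect on false clearance is small or conservative.

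A third objection is that ESA use has no documented dependence on iron status and is not a listed outcome. That is correct, and for ESA use the point is limited to undefined timing.

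**Conclusion.** The point holds and should be fixed. As written, the adjusted model can condition on a consequence of the regimen, so its OR may not estimate the total effect of the assigned schedule. That rests on the text alone.

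The size rests on assumptions and cannot be fixed from the document. With a true deficit of 20 points, linked transfusion moved the estimated difference to between −22 and −13 points in the main set of scenarios. Other assumed pathways widened this to about −23 to −11. The shift favours non-inferiority if transfusion mainly marks low iron. It is about nil or in the other direction if transfusion itself raises Ret-Hb enough. There is no bias if the regimen does not affect transfusion. Confidence is high that the covariate is badly specified; no claim is made that the trial's conclusion would change.

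**What to change.** Rewrite the covariate sentence in Data Analysis along these lines:

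- The adjusted model contains only factors fixed before randomisation: gestational age and in-born or out-born status.
- Post-randomisation transfusion and ESA use are not covariates. They are reported by arm as outcomes.
- Transfusion or ESA use before randomisation may be added only if its date is taken from the medical record and the event count allows. At the planned 80% replete, 100 infants give 100 × 0.20 = 20 who are not replete, so there is little room for extra terms.
- Any model containing on-study transfusion or ESA use is labelled exploratory, and the non-inferiority conclusion does not rest on it.

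The cost is a short text edit, and the sample size stays at 100. If pre-randomisation exposure is kept as a covariate, Data Collection also needs a dated field for it. The change should be made before any unblinded comparison, so that the choice of model cannot follow the results.
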